Change from Baseline in Patient Global Assessment (PGA) by visit

Proportion of subjects with GCA-related Health Resource Utilization by visit.

Proportion of subjects in remission at each visit through Week 52. Defined as:

- · Absence of GCA signs and symptoms
- Adherence to the protocol-defined CS taper regimen

Additional Endpoints for Period 2 are:

The following measures will be analyzed:

- Time to first disease flare from onset of Period 2 through Week 104. Disease flare is defined as an
 event determined by the investigator to represent recurrence of GCA signs or symptoms or an ESR
 measurement ≥ 30 mm/hr attributable to GCA AND requiring initiation of CS.
- Proportion of subjects maintaining remission from onset of Period 2 through Week 104. Remission is defined as absence of GCA signs and symptoms and CS-free.
- Cumulative CS exposure (Period 2 and inclusive of Periods 1 and 2) through Week 104
- Proportion of subjects in complete remission at Week 104. Complete remission is defined as having achieved all of the following:
 - Absence of GCA signs and symptoms;
 - Normalization of ESR (to < 30 mm/hr); if ESR ≥ 30 mm/hr and elevation is not attributable to GCA, this criterion can still be met;
 - Normalization of hsCRP (to < 1 mg/dL); and
 - CS-free.
- Proportion of subjects who experience at least 1 disease flare from onset of Period 2 through Week 104
- Number of disease flares per subject from onset of Period 2 through Week 104
- Change in SF-36 from onset of Period 2 through Week 104
- Change in FACIT-Fatigue from onset of Period 2 through Week 104
- Assessment of TSQM patient global satisfaction subscale from onset of Period 2 through Week 104
- Change in EQ-5D-5L from onset of Period 2 by visit through Week 104
- Assessment of PGIC from onset of Period 2 through Week 104
- Proportion of subjects with GCA-related Health Resource Utilization at Week 104.

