In Period 2, subjects who experience a flare (defined as an event determined by the investigator to represent recurrence of GCA signs or symptoms or an ESR measurement > 30 mm/hr attributable to GCA, AND requiring initiation of CS) will start open-label escape therapy with prednisone or prednisolone at investigator's discretion. A flare may be documented at either a scheduled or unscheduled visit. Subjects meeting flare criteria will return within approximately 4 weeks after the visit in which flare was determined for reassessment. The reassessment can occur at either a regularly scheduled or unscheduled visit. If the subject does not have absence of GCA signs and symptoms within approximately 4 weeks after the visit in which flare was determined, they will be discontinued from study drug. Subjects who discontinue study drug should receive treatment at the investigator's judgment, in accordance with local standard-of-care (which could include tocilizumab), and continue to follow the regular visit schedule for Period 2 and adhere to the study procedures as noted in Appendix D.

An independent, external data monitoring committee (DMC) will be established for periodic review of unblinded safety data and to ensure subject safety. In addition, a futility analysis will be conducted by the DMC to assess lack of efficacy once the first 140 enrolled subjects complete 24 weeks of treatment. Study sites and subjects will remain blinded for the duration of the study. After the last subject completes the Week 52 visit the Sponsor will be unblinded to Period 1 study drug assignment to facilitate regulatory filings. See Section 6.3 and Section 7.5 for additional details regarding the DMC and the planned futility analysis.

The schematic of the study is shown in Figure 1. Further details regarding study procedures are located in the Operations Manual.

See Section 5 for information regarding eligibility criteria.

[figure not shown]

Figure 1. Study Schematic

R1 = sustained remission for 24 consecutive weeks prior to Week 52; R2 = remission at Week 52 only

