Open-label prednisone or prednisolone will be provided until the dose is tapered to less than 20 mg/day. Subsequently, blinded CS therapy and/or matching CS PBO will be provided for the remaining blinded taper regimen. While receiving blinded CS therapy, subjects will receive 1 carton containing 3 bottles of CS study drug per week and will be instructed to take 1 capsule per bottle per day; the 3 capsules combined will be equivalent to the weekly dose according to the CS Tapering Schedule (Appendix E).

Corticosteroid Escape Therapy during the Study

Subjects who require CS escape therapy for their GCA disease will be deemed non-responders in the primary analysis. Any use of CS for escape therapy throughout the study will be documented in the eCRF.

Period 1:

At every visit, an assessment of subject's disease will be made to assess if the subject can adhere to the CS tapering schedule. If subject has no flare of GCA and is able to follow the CS tapering schedule, the subject will continue receiving protocol-defined blinded or open label CS therapy in the study.

In Period 1, disease flare is defined as an event determined by the investigator to represent recurrence of GCA signs or symptoms or an ESR measurement ≥ 30 mm/hr (attributable to GCA), AND requiring an increase in CS dose.

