by the investigator and dosing will be based on the investigator's judgment and in accordance with local standard of care. Medications prescribed by the investigator should be documented on the concomitant medication eCRF. Subjects who are discontinued from study drug during Period 1 should continue to follow the visit schedule for the remainder of Period 1 (Section 5.6).

Subjects who receive CS escape therapy will be eligible to continue in Period 2 if meeting criteria for study continuation outlined in Section 4.1.

Period 2

In Period 2, disease flare is defined as an event determined by the investigator to represent recurrence of GCA signs or symptoms or an ESR measurement ≥ 30 mm/hr, AND requiring initiation of CS. Subjects who experience disease flare in Period 2 (blinded extension phase) should receive an escape regimen of open-label prednisone or prednisolone at investigator's discretion. Thereafter, open-label escape CS taper will be based on the investigator's judgment and in accordance with local standard-of-care. At the investigator's discretion, these subjects may also discontinue study drug (upadacitinib or PBO and CS dispensed by Sponsor) and receive treatment in accordance with local standard-of-care, which may include tocilizumab, and should continue to follow the visit schedule for the remainder of Period 2 (Section 5.6). After discontinuation of study drug (upadacitinib or PBO and CS dispensed by Sponsor), CS will be prescribed by the investigator and dosing will be based on the investigator's judgment and in accordance with local standard of care. Medications prescribed by the investigator should be documented on the concomitant medication eCRF.

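### The Period 2 flare rule in Protocol 5.8 omits the condition, present in Protocol 4.1 and in the Period 2 flare endpoint definitions, that an ESR rise be attributable to GCA

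*Protocol*

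**What the plan says.** Two sections of the protocol tell sites when to start escape steroid in Period 2.

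- Protocol 4.1 gives the ESR limb of the rule as "ESR measurement > 30 mm/hr attributable to GCA, AND requiring initiation of CS) will start open-label escape therapy".
- Protocol 5.8, under the Period 2 part of the escape therapy text, gives "recurrence of GCA signs or symptoms or an ESR measurement ≥ 30 mm/hr, AND requiring initiation of CS". It then says: "Subjects who experience disease flare in Period 2 (blinded extension phase) should receive an escape regimen of open-label prednisone or prednisolone".

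The analysis definitions agree with 4.1 on attribution. Protocol 3.3 defines the Period 2 flare endpoint with an ESR "measurement ≥ 30 mm/hr attributable to GCA AND requiring initiation of CS". SAP 3.3 and SAP 9.5 also require attribution to GCA for the ESR limb.

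The Period 1 definition, earlier in the same Section 5.8, includes the condition: "an ESR measurement ≥ 30 mm/hr (attributable to GCA), AND requiring an increase in CS dose". No other sentence in 5.8 supplies it for Period 2.

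**The concern.** Sections 4.1 and 5.8 both direct treatment, so the difference is not simply one between an endpoint definition and a treatment rule. Because 5.8 states the attribution condition for Period 1 and leaves it out for Period 2, a site reading that section alone could take the omission as intended.

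Period 2 exists to compare continuing with withdrawing upadacitinib, and SAP 9.5 compares those treatment sequences. Under Protocol 3.3, Period 2 remission requires being CS-free, and cumulative steroid exposure through Week 104 is an endpoint. If some sites act on 5.8 and others on 4.1, the same clinical event may be recorded as a flare and given escape steroid at one site and not at another. The flare, remission and steroid results would then rest on a mixture of two rules.

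**Working it through.** There is no figure in the plan to reproduce and no arithmetic to do. The check is a comparison of the definitions, followed by test cases.

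**Step 1. The Period 2 flare definitions side by side.**

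| Place | Directs escape steroid? | ESR threshold (mm/hr) | Attribution to GCA required? | Start of steroid required? |
|---|---|---|---|---|
| Protocol 4.1 | Yes | > 30 | Yes | Yes |
| Protocol 5.8, Period 2 | Yes | ≥ 30 | **No** | Yes |
| Protocol 3.3 | No (endpoint) | ≥ 30 | Yes | Yes |
| SAP 3.3 and 9.5 | No (endpoint) | > 30 | Yes | Yes |

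All of them also leave the event to the investigator's determination. The threshold mismatch at exactly 30 is a separate matter. The cases below use an ESR of 45, so the threshold plays no part.

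**Step 2. Test cases for a Period 2 subject with ESR 45 mm/hr.**

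| Case | 4.1 | 5.8 | Protocol 3.3, SAP 3.3 and 9.5 |
|---|---|---|---|
| Attributed to GCA, steroid started | Flare | Flare | Flare |
| Not attributed to GCA, no GCA signs or symptoms, no steroid started | Not a flare | Not a flare | Not a flare |
| Not attributed to GCA, no GCA signs or symptoms, steroid started | Not a flare | **Can be a flare on the literal text** | Not a flare |

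Only the third case separates the sections.

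**Step 3. Can the third case occur?** Protocol 5.4 permits short-term systemic steroid during the study for non-GCA conditions, with serious infection among its examples. The Period 2 text in 5.8 does not say that the steroid must be started for GCA. Under Protocol 5.7 the Laboratory Assessor passes on any ESR above 30 without regard to cause. Attribution therefore has to be judged after notification, and the Period 2 text in 5.8 does not ask for that judgement.

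**Step 4. What differs downstream?** Under 4.1 and the analysis definitions, the third case is not a flare, and the steroid falls under the Protocol 5.4 limits (at most 10 days, and up to 100 mg prednisone or equivalent in total over Period 2). Under 5.8 the subject should receive an escape regimen at the investigator's discretion and may also be taken off study drug at the investigator's discretion. The endpoints open to the difference are time to first flare, proportion with a flare, number of flares, CS-free remission, complete remission at Week 104 and cumulative steroid exposure.

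**The case against.** The best defence is that context supplies the missing words. The escape therapy text in 5.8 opens by speaking of steroid needed for the subject's GCA, and 5.4 has a separate rule for non-GCA steroid. Every definition leaves the event to the investigator and requires that steroid be started. An investigator reading all of this would seldom call an infection-related ESR rise a GCA flare. The analysis definitions also agree with one another on attribution. Much of this stands: it limits how often the sections give different answers. It does not restore the condition to the Period 2 text, and it does not explain why the Period 1 text states it.

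A reader might infer two stronger points that the documents do not support.

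- **That a non-GCA ESR rise leads to mandatory stopping of study drug after the 4-week reassessment.** Protocol 4.1 stops study drug at that point only if GCA signs and symptoms are not absent. A subject with an ESR rise and no signs or symptoms would not meet that rule. Note b of the Activity Schedule also ties the post-flare visit to a GCA flare. Only the discretionary stopping in 5.8 remains.
- **That the effect can be sized from the six scheduled Period 2 ESR visits.** The documents give no rate of non-GCA ESR elevation. A calculation from an assumed rate would count subjects meeting the ESR limb, not flares or steroid courses. If it treated visits as independent, it would also ignore elevations that persist within a subject.

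**Conclusion.** The point holds as an inconsistency between two operative rescue rules, one of which also departs from the endpoint definitions. It rests on the literal wording of 5.8 and on the possibility that some sites follow that wording.

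Its reach is limited to additional Period 2 endpoints, which lie outside the multiplicity-controlled family. The Period 1 primary analysis and the controlled secondary endpoints are untouched. Flares already have one attribution rule for analysis. The remaining exposure is a flare declared, or escape steroid started, on the 5.8 wording for an event that the SAP would not count. Frequency is unknown and no magnitude is claimed. Whether attribution is already captured cannot be judged, because the eCRF and Operations Manual are not among the documents. A correction is worthwhile because it is cheap and Period 2 depends on when steroid is restarted.

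**What to change.** Reconcile the Period 2 text in Protocol 5.8 and the rule in Protocol 4.1 with the Period 2 flare definitions in Protocol 3.3 and SAP 3.3 and 9.5, so that one ESR attribution condition applies throughout. Which clinical rule is right is for the sponsor to decide and is not judged here.

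Send sites a short clarification. Confirm that the existing data collection records attribution for every ESR-triggered Period 2 flare, including those already declared, so that the SAP endpoints are derived on the single definition. A new field is needed only if that check shows a gap.

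The cost is a few words of protocol text, one site letter and a check of the eCRF specification. Design, sample size and Period 1 analyses do not change.

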5.9 Randomization/Drug Assignment and Blinding

All subjects will be assigned a unique identification number by the IRT at the Screening Visit. For subjects who rescreen, the screening number assigned by the IRT at the initial screening visit should be used. Subjects may only be rescreened one time without prior AbbVie approval. For additional re-screening, AbbVie TA MD approval is required.

All screening activities must be completed and reviewed prior to enrollment. Subjects who meet the eligibility criteria will proceed to enrollment via the IRT system on Day 1 (Baseline Visit of Treatment Period 1). The IRT will assign a randomization number that will encode the subject's treatment group assignment according to the randomization schedule generated by the statistics department at AbbVie. A subject number is assigned at screening via IRT. Enrolled subjects will keep their screening number as their subject number throughout the study.

This study is designed to enroll 420 subjects to meet scientific and regulatory objectives without enrolling an undue number of subjects in alignment with ethical considerations. Subjects in screening will be permitted to enroll even if the target number of subjects has been enrolled.

Randomization of all subjects, except for those in Japan, will be stratified by baseline CS dose (prednisone or prednisolone > 30 mg or \leq 30 mg), prior use of an IL-6 inhibitor, and whether entering the study with new onset or relapsing disease. In Japan, the study will attempt to include a minimum of 8 subjects; no stratification will be utilized for randomization, however, data on all 3 stratification factors will be collected. In Period 1, subjects will be randomized in a 2:1:1 ratio (upadacitinib 15 mg +

26-week CS taper regimen, upadacitinib 7.5 mg + 26-week CS taper regimen, or PBO + 52-week CS taper regimen).

In Period 2, subjects from the Period 1 upadacitinib group who achieve remission for at least 24 weeks prior to the Week 52 visit (at the end of Period 1) will be re-randomized to either continue on upadacitinib or switch to PBO (Section 4.1); re-randomization will be stratified by baseline disease status (new onset or relapsing disease). Subjects from the Period 1 Placebo group who achieve remission for at least 24 weeks prior to the Week 52 visit (at the end of Period 1) will continue to receive PBO. In Period 2, subjects previously on upadacitinib will be re-randomized in a 2:1 ratio (upadacitinib [same dose as Period 1] or PBO). Subjects who were assigned to PBO in Period 1 will continue to receive PBO. At Week 52, subjects who have absence of GCA signs and symptoms AND are CS-free, but do not meet the above remission criteria will continue in Period 2 on their originally randomized treatment assignment. All other subjects will be discontinued from study drug at the end of Period 1.

All AbbVie personnel with direct oversight of the conduct and management of the trial (with the exception of AbbVie Drug Supply Management Team) will remain blinded to each subject's treatment until the last subject completes the Week 52 visit. After the last subject completes the Week 52 visit the Sponsor will be unblinded to Period 1 and Period 2 study drug assignments to facilitate regulatory filings. The investigator, study site personnel, and the subject will remain blinded to each subject's treatment throughout the study. To maintain the blind, upadacitinib tablets and matching PBO tablets as well as CS capsules and matching PBO capsules provided for the study will be identical in appearance. The IRT will provide access to unblinded subject treatment information in the case of a medical emergency.

In the event of a medical situation that requires unblinding of the study drug assignment, the investigator is requested to contact the AbbVie TA MD prior to breaking the blind. However, if an urgent therapeutic intervention is necessary which warrants breaking the blind prior to contacting the AbbVie TA MD, the investigator can directly access the IRT system to break the blind without AbbVie notification or agreement. Unblinding is available in the IRT system via the Unblind Subject transaction, which is available only to the investigator. If the IRT system is unavailable, unblinding may occur by contacting the technical support of the IRT vendor via either phone (preferred) or email ([contact]). For country-specific phone numbers, please see the following website: (http://www.endpointclinical.com/help-desk/).

In the event that the blind is broken before notification to the AbbVie TA MD, we request that the AbbVie TA MD be notified within 24 hours of the blind being broken. The date and reason that the blind was broken must be conveyed to AbbVie and recorded on appropriate eCRF.

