6.2 Toxicity Management

The toxicity management of the AEs including AEs of special interest consists of safety monitoring (review of AEs on an ongoing basis, and periodical/ad hoc review of safety issues by a safety data monitoring committee), and if applicable, interruption of study drug dosing with appropriate clinical management and/or discontinuation of the subjects from study drug. The management of specific AEs and laboratory parameters is described below.

For subjects who discontinue study drug but continue study participation and are on standard of care therapies, these toxicity management requirements do not apply (including alerts from the central lab) and any intolerability to standard of care therapies should be managed by the prescribing physician.

Serious Infections: Subjects should be closely monitored for the development of signs and symptoms of infection during and after treatment with study drug. Study drug should be interrupted if a subject develops a serious infection. A subject who develops a new infection during treatment with study drug should undergo prompt diagnostic testing appropriate for an immunocompromised subject. As appropriate, antimicrobial therapy should be initiated, and the subject should be closely monitored. Study drug may be restarted once the infection has been successfully treated. Subjects who develop active TB must be permanently discontinued from study drug.

Herpes Zoster: If a subject develops herpes zoster, consider temporarily interrupting study drug until the episode resolves.

Gastrointestinal Perforation: Subjects presenting with the onset of signs or symptoms of a gastrointestinal perforation should be evaluated promptly for early diagnosis and treatment. If the diagnosis of gastrointestinal perforation (other than due to appendicitis or mechanical injury) is confirmed, the subject must be permanently discontinued from study drug.

Major Cardiovascular Event: For subjects who develop a major cardiovascular event (MACE: acute myocardial infarction, cerebrovascular accident [stroke]) while on study drug, the investigator should

evaluate the benefit/risk of, and discuss with the TA MD whether it is appropriate to continue study drug.

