7 STATISTICAL METHODS & DETERMINATION OF SAMPLE SIZE

7.1 Statistical and Analytical Plans

An unblinded analysis for Period 1 will be conducted after all subjects have completed Week 52 or have prematurely discontinued the study prior to Week 52. An unblinded analysis for Period 2 will be conducted after all subjects have completed Week 104 or have prematurely discontinued the study prior to Week 104. Additional unblinded analysis in Period 2 may be conducted for regulatory purposes. To maintain integrity of the trial and avoid introduction of bias, study sites and subjects will remain blinded until all subjects have completed Period 2 (Week 104).

Statistical analyses will be described and fully documented in the Statistical Analysis Plan (SAP). The statistical analyses will be performed using SAS (SAS Institute Inc., Cary, North Carolina, USA).

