2.2 Study Design Overview

Study M16-852 is a Phase 3, global, multicenter, randomized, double-blind, placebo-controlled study to evaluate the safety and efficacy of upadacitinib in subjects with GCA.

The study is designed to enroll approximately 420 subjects to meet scientific and regulatory objectives without enrolling an undue number of subjects in alignment with ethical considerations. Subjects in screening will be permitted to enroll even if the target number of subjects has been enrolled. The study population will consist of adult subjects who are at least 50 years of age with a diagnosis of active GCA, either new onset or relapsing disease, within 8 weeks of Baseline.

The study will allow enrollment of a minimum of 30% of subjects with new onset disease and up to 70% of subjects with relapsing disease. The study will also allow enrollment of up to 20% of subjects with previous use of an IL-6 inhibitor with discontinuation based on reasons other than disease flare.

The Primary Analysis will be conducted after all subjects have completed the Week 52 visit or have prematurely discontinued from the study prior to the Week 52 visit. The Primary Analysis will include efficacy and safety data in Period 1 and safety data in Period 2 up to the data cut-off date for the Primary Analysis. The final analysis will be

conducted after all subjects have completed the Week 104 visit and the safety Follow-up Visit or have prematurely discontinued from the study.

An independent, external data monitoring committee (DMC) will be established for periodic review of unblinded safety data and to ensure subject safety. In addition, a futility analysis will be conducted by the DMC to assess lack of efficacy once the first 140 enrolled subjects complete 24 weeks of treatment. Study sites and subjects will remain blinded for the duration of the study.

After all subjects have either completed the Week 52 visit or have prematurely discontinued from the study prior to the Week 52, the Sponsor will be unblinded to Period 1 and Period 2 study drug assignment to perform the Primary Analysis and facilitate potential regulatory filings. The investigator, study site personnel, and the subject will remain blinded to each subject's treatment throughout the study.

A schematic of the study is shown in Figure 1.

[figure not shown]

Figure 1. Study Schematic

[figure not shown]

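### Protocol 4.1 differs from Protocol 5.9 and SAP 2.2 on whether the sponsor is unblinded to Period 2 after the last Week 52 visit, and no site-facing sponsor role is said to stay blinded while Period 2 runs.

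*Protocol*

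**What the plan says.** Three current passages set the scope of sponsor unblinding at what is in effect one milestone.

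- Protocol 4.1: "After the last subject completes the Week 52 visit the Sponsor will be unblinded to Period 1 study drug assignment to facilitate regulatory filings". Period 2 is not mentioned.
- Protocol 5.9: "the Sponsor will be unblinded to Period 1 and Period 2 study drug assignments to facilitate regulatory filings". The same paragraph says that sponsor personnel with direct oversight of the trial, apart from the drug supply team, "will remain blinded to each subject's treatment until the last subject completes the Week 52 visit".
- SAP 2.2: "the Sponsor will be unblinded to Period 1 and Period 2 study drug assignment to perform the Primary Analysis and facilitate potential regulatory filings".

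After that milestone, only investigators, site personnel and subjects are named as still blinded (Protocol 5.9 and 7.1, SAP 2.2). Period 2 is a 52-week blinded extension. Upadacitinib subjects in remission for at least 24 weeks are re-randomised 2:1 at Week 52 to stay on their dose or switch to placebo.

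The sponsor keeps some contact with sites in Period 2. After a major cardiovascular event, the investigator is to "discuss with the TA MD whether it is appropriate to continue" study drug (Protocol 6.2). Protocol 6.2 also directs investigators to the sponsor's Therapeutic Area Medical Director (TA MD) about certain liver enzyme elevations and to the medical monitor about symptomatic CPK elevation. Protocol 9 has sponsor personnel review the eCRFs periodically.

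**The concern.** Staff reading 4.1 and staff reading 5.9 could reach different conclusions about who may see the Period 2 codes. If 5.9 governs, the people who advise sites and review their data may know whether a given subject was kept on upadacitinib or withdrawn while that subject's Period 2 outcome is still accruing.

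Continuing versus withdrawing upadacitinib is a stated objective (Protocol 3.1), and SAP 9.5 compares the treatment sequences. Protocol 7.1 keeps sites and subjects blinded in order to protect trial integrity and avoid bias. The same reasoning applies to sponsor staff who influence decisions on study drug or the handling of data. The sponsor has also recognised this route: Appendix F explains the removal of the TA MD's power to mandate discontinuation of a subject as a way to limit bias.

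**Working it through.** The scope question needs no formula. It is settled by comparing the passages. Arithmetic enters only for the number of subjects affected.

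**1. Scope.** Protocol 4.1 covers Period 1. Protocol 5.9 and SAP 2.2 cover Periods 1 and 2. All three are current text, so this is not a difference between the plan and its amendment log.

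**2. Who loses the blind.** Protocol 5.9 protects sponsor personnel with direct oversight only up to the last Week 52 visit. No later passage in the supplied documents names a sponsor role that stays blinded.

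**3. What the Period 2 codes add.** Placebo subjects who continue stay on placebo, and subjects who miss the 24-week remission criterion but qualify to continue keep their original assignment. Period 1 codes therefore already reveal the Period 2 treatment of both groups. For a re-randomised subject, Period 1 codes leave a 2/3 chance of upadacitinib and a 1/3 chance of placebo. Period 2 codes remove that uncertainty. The difference between 4.1 and 5.9 is exactly the continue-versus-withdraw assignment.

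**4. Which endpoints are open to influence.** SAP 8.0 treats remission endpoints as non-response after premature discontinuation of study treatment, and SAP 9.5 carries similar handling into Period 2. Two of the twelve Period 2 endpoints in SAP 3.3 are remission endpoints: remission maintained through Week 104, and complete remission at Week 104. Under the carried-over rules, flare endpoints, cumulative CS exposure and the change-from-onset scores use data regardless of discontinuation, so stopping drug is not itself failure there.

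**5. How many subjects.** Let accrual last A weeks at an even rate, with full retention and the same chance of entering Period 2 throughout. Unblinding falls at week A + 52. A subject randomised at week s reaches Week 104 at s + 104 and is still in Period 2 if s > A − 52. The share is 52/A. Time remaining is spread evenly from 0 to 52 weeks, so it averages 26 weeks, or 26/52 = half of Period 2.

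| Accrual (assumed) | Share of entrants still in Period 2 | Share of all Period 2 time after unblinding |
|---|---|---|
| 3.5 years, 182 weeks | 52/182 = 29% | 0.29 × 0.5 = 14% |
| 5 years, 260 weeks | 52/260 = 20% | 0.20 × 0.5 = 10% |

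The documents anchor the long end only. The first randomisation was on 06 Feb 2019 (SAP Appendix H), and the SAP dated 14 Feb 2024 reports 428 enrolled (SAP 9.1). That interval is 1,834 days, or 262 weeks. If 428 is the final total, accrual cannot have been longer, and with even accrual the share is at least 52/262 = 20%. The 3.5-year figure has no source in the documents.

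**The case against.** The strongest reply is that 4.1 is an incomplete summary sentence and the intent is clear elsewhere. Protocol 5.9 and SAP 2.2 agree, Protocol 7.1 allows further unblinded Period 2 analyses for regulatory purposes, and the primary analysis needs Period 2 codes. SAP 2.2 includes Period 2 safety data, SAP 10.1 summarises safety by treatment group, and the long-term safety set in SAP 4.0 requires the same drug in both periods. This stands. A reader might infer that 4.1 promises to keep Period 2 hidden from the sponsor. It does not say so, and making 5.9 and the SAP match that reading would conflict with the planned outputs.

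The reply also limits the consequences, and most of those limits stand:

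- Investigators, who judge flares, remain blinded, and Protocol 5.5 gives the sponsor no power to stop an individual subject's drug. The sponsor contacts in Protocol 6.2 concern safety events.
- A reader might infer that unblinded deviation review could shape the Period 2 analysis sets. It could not. The Per-Protocol set is a subset of FAS1 and is fixed before the primary lock, while FAS2 depends on Period 1 remission and one dose in Period 2.
- Period 2 endpoints lie outside the multiplicity procedure, and Protocol 7.3 plans descriptive statistics for them.
- The Operations Manual was not among the supplied documents and may contain access controls.

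None of this reconciles the three passages or names a sponsor role that stays blinded.

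**Conclusion.** The point holds in a limited form. The inconsistency is plain on the text. Under the wider wording, sponsor staff who still advise sites and review data could know the re-randomised arm for up to 52 weeks of ongoing follow-up. That they would know it is an inference from 5.9 and from the absence of any stated separation, and a document not supplied could change it.

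The exposure is to the Period 2 additional endpoints, mainly the two remission endpoints. With even accrual over 3.5 to 5 years, full retention and a constant chance of entry, about 20–29% of Period 2 entrants would still be in Period 2 at unblinding, or 10–14% of all Period 2 time. Only the re-randomised subjects among them are newly exposed, and the documents do not give their number.

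A reader might infer that the trial's main result is at risk. The documents do not support that: by this milestone every subject has completed Week 52 or left, so the primary and multiplicity-controlled comparisons are unaffected. The point should be corrected for the sake of the continue-versus-withdraw objective.

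**What to change.** Give Protocol 4.1, Protocol 5.9 and SAP 2.2 the same rule, in two parts:

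1. At the primary analysis, Period 2 codes are released only to the personnel who produce the planned Period 2 safety outputs and the filing.
2. Site-facing sponsor roles (the TA MD, medical monitor, site monitors and data management) stay blinded to individual re-randomised Period 2 assignments until the Week 104 lock. The emergency unblinding route in 5.9 is unchanged.

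If the Operations Manual already restricts access in this way, a cross-reference is enough. The cost is a wording change and access control. Treatment, visits and sample size do not change. The small downside is that the site-facing roles see subject-level Period 2 data by arm later.
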